8.3.2. Clinical Laboratory Evaluations

For continuous laboratory parameters, values and their changes from baseline at each visit will be summarized, as well as the maximum and minimum post-treatment values, and values for the last observation on treatment. Last observation on treatment is defined as the last non-missing value on or prior to end of treatment duration plus 7 days.

Repeated or unscheduled tests will not be summarized for each scheduled visit, but will be included for summaries of maximum and minimum post-treatment values.

Clinical laboratory test results (hematology and blood chemistry) will be graded according to the NCI CTCAE, Version 4.03. Test results will also be flagged as low or high relative to the normal reference ranges. For each test, subjects will be characterized based on their worst severity grade observed during post-baseline period, based on CTCAE criteria and/or normal reference ranges. For parameters where CTCAE criteria are applicable, a shift table presenting the 2-way frequency tabulation of baseline and the worst post-baseline CTCAE grades will be provided. If absolute neutrophil or lymphocyte counts are not reported in the lab data, but percent differentials and total WBC are available, the absolute counts will be derived by the formula: differential count = $100 \times \text{differential}(\%) / \text{WBC}$ and will be reported with the same units as WBC. Derived differentials will be used for NCI-CTCAE toxicity grading, and will not be reported with a normal range. Derived values that do not meet the NCI-CTCAE criteria for grade 2 or higher toxicity will be reported as grade <1 and as being within normal range. If the result of a liver function test is below a certain threshold (e.g., AST reported as <10), then it will be reported as grade <1 and as being within normal range.

Abnormal clinical laboratory test results deemed of clinical significance or of CTCAE Grade 3 or 4 will be listed.

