5.2.2. Clinical Laboratory Evaluations

Safety laboratory assessments will include hematology, serum chemistry, coagulation, and urinalysis.

- Coagulation (only at Screening): prothrombin time, international normalized ratio, and partial thromboplastin time
- Hematology: CBC including hemoglobin, hematocrit, white blood cell count (WBC) with 5 part differential (including absolute neutrophil count), red blood cell, and platelet count
- Serum chemistry: bicarbonate, calcium, phosphorus, magnesium, albumin, glucose, serum creatinine, uric acid, total protein, urea, AST, ALT, lactic dehydrogenase, alkaline phosphatase, total and direct bilirubin, sodium, potassium, and chloride
- Routine urinalysis: dipstick and microscopy (if indicated), including protein, specific gravity, glucose, and blood
- Serum or urine β -HCG pregnancy test

At Screening, creatinine clearance (mL/min) or GFR will be calculated. This will also be done before each cisplatin or carboplatin administration.

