Programming Note: continue for HRG Low and Overall on the next page

Daiichi Sankyo Pharma Development
Protocol U31278-A-U203

Page x of y

<Run Type> (Data Cut Date: DDMMYY; Data Extraction Date: DDMMYY)

<programe> <run date time>

The following table follows Table 15.3.4.1:

Table 15.3.4.2: Summary of Results and Change from Baseline in Laboratory Tests - Chemistry
Safety Analysis Set

Source Data: adam.adlb; Listing 16.2.8.1.2

Approved

<Run Type> (Data Cut Date: DDMMYYYY; Data Extraction Date: DDMMYYYY)

Table 15.3.4.3: Shift Table of CTCAE Grade in Laboratory Tests – Hematology
 Safety Analysis Set

HRG High

Condition (Unit) Treatment	Baseline CTCAE Grade	Worst Post-baseline CTCAE Grade						Total n (%)	Missing n
		< 1 n (%)	1 n (%)	2 n (%)	3 n (%)	4 n (%)	3 or 4 n (%)		
Condition #1									
Patritumab+ cetuximab + cisplatin or carboplatin (n=xxx)		xx (xx.x%)	xx (xx.x%)	xx (xx.x%)	xx (xx.x%)	xx (xx.x%)	xx (xx.x%)	xx (xx.x%)	
	< 1								xx
	1	xx (xx.x%)	xx (xx.x%)	xx (xx.x%)	xx (xx.x%)	xx (xx.x%)	xx (xx.x%)	xx (xx.x%)	xx
	2	xx (xx.x%)	xx (xx.x%)	xx (xx.x%)	x (xx.x%)	xx (xx.x%)	xx (xx.x%)	xx (xx.x%)	xx
	3	xx (xx.x%)	xx (xx.x%)	xx (xx.x%)	xx (xx.x%)	xx (xx.x%)	xx (xx.x%)	xx (xx.x%)	xx
	4	xx (xx.x%)	xx (xx.x%)	xx (xx.x%)	xx (xx.x%)	xx (xx.x%)	xx (xx.x%)	xx (xx.x%)	xx
	3 or 4	xx (xx.x%)	xx (xx.x%)	xx (xx.x%)	xx (xx.x%)	xx (xx.x%)	xx (xx.x%)	xx (xx.x%)	xx
	Total	xx (xx.x%)	xx (xx.x%)	xx (xx.x%)	xx (xx.x%)	xx (xx.x%)	xx (xx.x%)	xx (xx.x%)	xx
	Missing	xx	xx	xx	xx	xx	xx	xx	xx
Placebo + cetuximab + cisplatin or carboplatin (n=xxx)									
	< 1								xx
	1	xx (xx.x%)	xx (xx.x%)	xx (xx.x%)	xx (xx.x%)	xx (xx.x%)	xx (xx.x%)	xx (xx.x%)	xx
	2	xx (xx.x%)	x (x.x%)	xx (xx.x%)	xx (xx.x%)	xx (xx.x%)	xx (xx.x%)	xx (xx.x%)	xx
	3	xx (xx.x%)	xx (xx.x%)	xx (xx.x%)	xx (xx.x%)	xx (xx.x%)	xx (xx.x%)	xx (xx.x%)	xx
	4	xx (xx.x%)	xx (xx.x%)	xx (xx.x%)	xx (xx.x%)	xx (xx.x%)	xx (xx.x%)	xx (xx.x%)	xx
	3 or 4	x (xx.x%)	xx (xx.x%)	xx (xx.x%)	xx (xx.x%)	xx (xx.x%)	xx (xx.x%)	xx (xx.x%)	xx
	Total	xx (xx.x%)	xx (xx.x%)	xx (xx.x%)	xx (xx.x%)	xx (xx.x%)	xx (xx.x%)	xx (xx.x%)	xx
	Missing	x	xx	xx	xx	xx	xx	xx	xx
Condition #2 . . . etc.									

Notes: The baseline value is defined as the last non-missing value before initial administration of study treatment.

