Listing 16.2.7.4: Adverse Event Leading to Study Drug Interruption or Dose Reduction
Safety Analysis Set

Listing 16.2.7.5: Adverse Events of Interests
Safety Analysis Set

Approved

Daiichi Sankyo Pharma Development
 Protocol U31287-A-U203
 <Run Type> (Data Cut Date: DDMMYY; Data Extraction Date: DDMMYY)

Page x of y
 <programe> <run date time>

Listing 16.2.8.1.1: Laboratory Data – Hematology
 Safety Analysis Set

HRG High

Subject ID/ Group/Age/ Gender	Lab Name	Parameter (Standard Units)	Visit	Date/Time of Sample (Day)	Result [a]	Normal Limits	Change from Baseline	CTC Grade
xxxxxx/ Patritumab+ cetuximab + cisplatin or carboplatin/ xx/F	xxxxxxxxxx	Test #1 (xxxxx)	Screening	yyyy-mm-dd hh:mm (xx)	xxxx	xxxx-xxxx		
			CxDx	yyyy-mm-dd hh:mm (xx)	xxxx (H)	xxxx-xxxx	xxxx	x
			CxDx	yyyy-mm-dd hh:mm (xx)	xxxx	xxxx-xxxx	xxxx	
		Test #2 (xxxxx)	Screening	yyyy-mm-dd hh:mm (xx)	xxxx	xxxx-xxxx		
			CxDx	yyyy-m -dd hh:mm (xx)	xxxx	xxxx-xxxx	xxxx	
			CxDx	yyyy-mm-dd h:mm (xx)	xxxx	xxxx-xxxx	xxxx	

APPROVED

Notes: [a] H = Abnormally High, L = Abnormally Low

Source: adam.adlb
 Programming Note: continue for HRG Low and Overall on the next page

Daiichi Sankyo Pharma Development
Protocol U31287-A-U203

Page x of y

<programe> <run date time>

<Run Type> (Data Cut Date: DDMMYYYY; Data Extraction Date: DDMMYYYY)

These Appendices follow Listing 16.2.8.1.1:

Listing 16.2.8.1.2: Laboratory Data – Chemistry
Safety Analysis Set

Listing 16.2.8.1.3: Laboratory Data – Urinalysis
Safety Analysis Set

Programming Notes: Remove Change from baseline and CTC grade columns for urinalysis.

Listing 16.2.8.1.4: Laboratory Data – Coagulation
Safety Analysis Set

Listing 16.2.8.2.1: Clinically Significant Laboratory Abnormalities or Abnormalities of CTCAE Grade 3 or 4 – Hematology
Safety Analysis Set

Listing 16.2.8.2.2: Clinically Significant Laboratory Abnormalities or Abnormalities of CTCAE Grade 3 or 4 – Chemistry
Safety Analysis Set

Approved

Daiichi Sankyo Pharma Development
 Protocol U31287-A-U203

Page x of y
 <programe> <run date time>

<Run Type> (Data Cut Date: DDMMYY; Data Extraction Date: DDMMYY)

Listing 16.2.8.2.3 Subjects with Liver Enzymes (ALT, AST) and Total Bilirubin (TBL) Elevation
 Safety Analysis Set

HRG High

Subject ID/ Group/Age/ Gender	Investigator/ Country/Site	Visit	Date/Time of Sample (Day)	AST (xxx-xxx) [a]	ALT (xxx-xxx) [a]	Total Bilirubin (xxx-xxx) [a]	ALP (xxx-xxx) [a]

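### SAP 8.3.2 inverts the fallback formula for absolute neutrophil and lymphocyte counts, so derived counts would be wrong and low neutrophil counts could be graded as normal

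*SAP*

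**What the plan says.** SAP 8.3.2 (Clinical Laboratory Evaluations) sets a fallback for hematology records: "If absolute neutrophil or lymphocyte counts are not reported in the lab data, but percent differentials and total WBC are available", then "the absolute counts will be derived by the formula: differential count" = 100 × differential(%) / WBC. Three further statements in that section govern the result:

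- Units: "and will be reported with the same units as WBC".
- Use: "Derived differentials will be used for NCI-CTCAE toxicity grading", with no normal range reported beside the value.
- Default: derived values that do not meet the criteria "for grade 2 or higher toxicity will be reported as grade <1 and as being within normal range".

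The graded values go to the hematology shell "Shift Table of CTCAE Grade in Laboratory Tests" (Table 15.3.4.3) and to the listing "Clinically Significant Laboratory Abnormalities or Abnormalities of CTCAE Grade 3 or 4" (Listing 16.2.8.2.1). No other section gives a different formula, and SAP section 9 records no changes. SAP 8.3.2 does not fix the unit of WBC; the shell for Table 15.3.4.1 refers to SI units.

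**The concern.** The formula and the unit statement cannot both be right. A percentage divided by WBC has units of 1/WBC. The printed expression has the form of the reverse calculation (percentage = 100 × count / WBC), so a transposition is the likely cause.

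The error acts in a harmful direction. At a fixed percentage, a lower WBC gives a higher derived count, so the most leukopenic patients get the largest values. The default rule then labels a falsely high neutrophil count as normal, with no reference range beside it to expose the mistake. Protocol 5.1.7.2 warns that severe leukopenia and neutropenia may be more frequent when cetuximab is given with platinum, so neutrophil grade is a core safety output here.

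**Working it through.** The SAP gives no worked value to reproduce, so the check is a unit check followed by direct arithmetic.

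**Inputs.** The printed formula and default rule are from SAP 8.3.2. The reference for a low neutrophil count is 1.5 × 10^9/L, the minimum in Protocol 5.1.7.1 for receiving patritumab. Protocol 5.1.7.3 states WBC in 10^9/L. The example WBC and percentage values are assumptions chosen to span low to high counts.

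**Formulas.** With W = WBC and p = differential in percent:

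- Correct: W × p / 100.
- Printed: 100 × p / W.
- Ratio, printed to correct: 10,000 / W². For p > 0 the two agree only at W = 100 in whatever unit is used. At p = 0 both give 0.

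**WBC in 10^9/L.**

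| W | p (%) | Correct count | Printed formula |
|---|---|---|---|
| 2.0 | 20 | 2.0 × 20 / 100 = 0.40 | 100 × 20 / 2.0 = 1000 |
| 1.5 | 30 | 0.45 | 2000 |
| 1.0 | 40 | 0.40 | 4000 |
| 20 | 3 | 0.60 | 15 |
| 30 | 1 | 0.30 | 3.33 |
| 2.0 | 10 (lymphocytes) | 0.20 | 500 |

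The ratio is 10,000 at W = 1, 2,500 at W = 2, 156 at W = 8, 25 at W = 20 and 11 at W = 30.

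**Grid.** For W from 0.5 to 30.0 in steps of 0.1 (296 values) and p from 1 to 100 in whole percents, 5,402 combinations have a correct count below 1.5. The printed formula gives at least 3.33 in every one (minimum at W = 30, p = 1), so none looks low.

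**WBC in cells/mm³.** The error reverses. W = 7000 with 60% is 4200, but the printed formula gives 100 × 60 / 7000 = 0.86. For W from 4000 to 11000 and p from 40 to 80, correct counts run from 1600 to 8800 and printed values from 0.36 to 2.0. Ordinary counts would look severely low.

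**Other readings.** Entering the differential as a fraction does not help: W = 5.0 with 0.60 gives 100 × 0.60 / 5.0 = 12, not 3.0. Moving the 100 to the denominator gives 60 / (100 × 5.0) = 0.12, also not 3.0.

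**The case against.** The strongest reply is that the rule may hardly ever run. SAP 5.2.2 plans a white cell count "with 5 part differential (including absolute neutrophil count", Protocol 9.7 does the same, and Protocol 5.1.7.1 requires the neutrophil count before patritumab is given. This stands as a limit on scope: the documents do not say how many records would need derivation, and there may be few. Those provisions name neutrophils only; no equivalent safeguard is stated for absolute lymphocyte counts.

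A second reply is that the error would expose itself, because a neutrophil count of 1000 cannot come from a WBC of 2.0. That is often true but not always: W = 20 with 3% gives 15, and W = 30 with 1% gives 3.33, both below the total WBC. A programmer who did notice would have to depart from the approved SAP, and SAP section 1 requires deviations to be justified in writing.

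A third reply is that severe neutropenia has other routes into the report. Protocol 9.7 asks for Grade 3 or higher laboratory values to be recorded as adverse events, the Grade 3/4 listing also takes results judged clinically significant, and total WBC is reported separately from this formula. These routes partly protect the safety conclusions. They do not correct the laboratory tables.

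Finally, the cells/mm³ case is secondary, since the shells point to SI units. It matters only because SAP 8.3.2 leaves the unit open. For lymphocytes, the derived value is plainly wrong, but the documents do not show what grade a grossly high value would receive.

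**Conclusion.** The formula is wrong as written and should be corrected. Its scope is limited to records without a reported absolute count; reported counts and all efficacy analyses are unaffected.

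Within that scope, with WBC in 10^9/L, a derived count is overstated by a factor of 10,000 / WBC², and every low neutrophil count on the grid is returned at 3.3 or more. Such a record would appear as grade <1 in the shift table and would not reach the Grade 3/4 listing on grade. It would also distort the summaries in Table 15.3.4.1.

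The statement about missed grades rests on one assumption: the documents print no CTCAE cut-offs, and Grade 2 or higher neutropenia is taken to lie at or below 1.5 × 10^9/L. The finding that the formula is inverted needs no assumption.

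**What to change.** In SAP 8.3.2, replace the formula with: absolute count = WBC × differential(%) / 100, in the units of WBC. Add that WBC is converted to 10^9/L before CTCAE grading. The corrected formula alone restores the stated units; the conversion sentence closes the gap left by the unspecified WBC unit. The cost is one formula and one unit statement, with no change to data collection.

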**Table 5.5: Cisplatin Dose Modifications and Discontinuations\* for Toxicities**

Toxicity	Dose Modification/Discontinuation
Hematological	A repeat course should not be given until circulating blood elements are at an acceptable level (ie, platelets $\geq 100 \times 10^9/L$ , white blood cells $\geq 4 \times 10^9/L$ )
Febrile neutropenia/infection	The first episode of febrile neutropenia or infection will result in reduction by 20% of cisplatin dose. If there is a second episode, despite dose reduction, the subject must receive prophylactic antibiotics during subsequent cycles. If there is a third episode, the subject will be withdrawn from study.
Neutropenia	Grade 2 or 3: cisplatin treatment delay until < Grade 1. Grade 4: cisplatin treatment delay until < Grade 1; dose reduction of all further doses of cisplatin by 20%.
Nephrotoxicity	A repeat course of cisplatin should not be given until the serum creatinine is below 1.5 mg/100 mL, and/or the urea is below 25 mg/100 mL
Thrombocytopenia	Grade 1: cisplatin treatment delay until platelets $\geq 100,000/mm^3$ . $\geq$ Grade 2: cisplatin treatment delay until platelets $>100,000/mm^3$ , dose reduction of all further doses of cisplatin by 20%

Toxicity	Dose Modification/Discontinuation
Organ Toxicity	Grade 2: Delay chemotherapy until $\leq$ Grade 1. $\geq$ Grade 3 or more: Delay chemotherapy until $\leq$ Grade 1; dose reduction of all further doses of cisplatin by 20%. Do not delay or reduce cisplatin dose if there are asymptomatic increases in transaminases, cetuximab-induced skin reactions, and subclinical side effects (e.g. nausea, vomiting, alopecia, altered taste).
Ototoxicity	Criteria for hearing testing
Neuropathy	In case of sensory neuropathy $\geq$ Grade 2, change cisplatin to carboplatin

Note: Please refer to the cisplatin package insert for additional information on potential toxicities and their management. When cisplatin is administered in combination with other agents such as cetuximab, refer to their respective product information. \*If events do not recover within 3 weeks, discontinue cisplatin treatment.

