### **11.6.2. Clinical Laboratory Evaluation Analyses**

Clinical laboratory data and their changes from baseline (only for continuous laboratory parameters) will be summarized by treatment group and visit (including the maximum and minimum post-treatment values and the values at the End of Treatment visit). Summary tables will be presented for each relevant assay to show the number of subjects by CTCAE severity grade with corresponding percentages. For parameters for which a CTCAE scale does not exist, the frequency of subjects with values below, within, and above the normal ranges will be summarized by treatment. Subjects will be characterized only once for a given assay, based on their worst severity grade observed during the time period of interest. Shift tables for clinical laboratory data will also be presented showing change in CTCAE severity grade from baseline to each visit (and to the minimum, maximum, and last post-baseline values) for each treatment.

Laboratory test results (hematology and blood chemistry) will be graded according to the NCI CTCAE, Version 4.03. A shift table, presenting the two-way frequency tabulation for baseline and the worst post-treatment value according to the CTCAE grade, will be provided for clinical laboratory tests. Abnormal clinical laboratory test results deemed of clinical significance or of Grade 3 or 4 will be listed.

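### SAP 8.3.2 leaves no way for a derived neutrophil or lymphocyte count to be Grade 1: anything below Grade 2 is tabulated as grade <1 and normal

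*SAP*

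**What the plan says.** SAP 8.3.2 sets the general standard: "Clinical laboratory test results (hematology and blood chemistry) will be graded according to the NCI CTCAE, Version 4.03". Protocol 11.6.2 says the same, with no exception for derived counts: "Laboratory test results (hematology and blood chemistry) will be graded according to the NCI CTCAE, Version 4.03". SAP section 9 records no changes from the protocol's analyses.

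SAP 8.3.2 then adds a special rule for white-cell differentials. Its trigger is: "If absolute neutrophil or lymphocyte counts are not reported in the lab data, but percent differentials and total WBC are available". Both the percentage and the WBC are needed; without the WBC nothing is derived. The count is then computed as 100 × differential (%) / WBC and labelled with the WBC units. On its use the SAP says: "Derived differentials will be used for NCI-CTCAE toxicity grading, and will not be reported with a normal range". The next sentence sets the default: those derived counts which "do not meet the NCI-CTCAE criteria for grade 2 or higher toxicity will be reported as grade <1 and as being within normal range".

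The same section flags results low or high against reference ranges and calls for a shift table of baseline against worst post-baseline grade. The shell for that table (Table 15.3.4.3) gives <1 and 1 separate rows and separate columns. Listing 16.2.8.1.1 prints result, normal limits and CTC grade by visit.

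**The concern.** The default sentence merges two categories that the output tables keep apart. A derived count is either Grade 2 or higher, or it is <1; Grade 1 is not an available outcome. The identical count reported directly by another laboratory would go through ordinary CTCAE grading and range flagging and could come out as Grade 1 and low. The hematology tables would then mix two grading rules, according to how the laboratory reports its differential, and nothing in the table would show it.

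The second problem is internal to the paragraph. A value with no normal range attached cannot be declared inside one. The honest statement for such a value is that its position relative to the lower limit is unknown.

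What is at stake is descriptive: mild neutropenia and lymphopenia would be under-counted, and a mildly low baseline would be shown as normal.

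**Working it through.** The plan gives no figure to reproduce, and the core of the point needs no outside number.

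**Step 1. Possible grades.** For a directly reported count, Table 15.3.4.3 allows <1, 1, 2, 3, 4. For a derived count, the default sentence sends everything not Grade 2 or higher to <1. The possible grades are then <1, 2, 3, 4. Every derived Grade 1 value is misplaced, wherever the Grade 1 limits lie.

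**Step 2. Worked neutrophil counts.** The CTCAE table and laboratory limits are not in the documents, so these are assumptions: Grade 2 starts below 1.5 ×10⁹/L, and Grade 1 runs from there up to a lower limit of normal of 1.8 to 2.0 ×10⁹/L. Correct count = WBC × % / 100. Printed formula = 100 × % / WBC.

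| WBC | % | Correct count | Grade at either assumed limit | Default rule on correct count | Printed formula |
|---|---|---|---|---|---|
| 6.0 | 60 | 3.60 | <1 | <1, normal | 1000 |
| 4.0 | 42 | 1.68 | 1 | <1, normal | 1050 |
| 4.0 | 40 | 1.60 | 1 | <1, normal | 1000 |
| 3.2 | 50 | 1.60 | 1 | <1, normal | 1562.5 |
| 3.0 | 40 | 1.20 | ≥2 | ≥2 | 1333 |
| 2.5 | 30 | 0.75 | ≥2 | ≥2 | 1200 |
| 2.0 | 20 | 0.40 | ≥2 | ≥2 | 1000 |
| 1.0 | 10 | 0.10 | ≥2 | ≥2 | 1000 |

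With the count computed correctly, the three Grade 1 rows are lost and the Grade 2 or higher rows are kept. Correcting the formula alone therefore does not restore Grade 1.

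**Step 3. Interaction with the printed formula.** The formula is inverted. Taken literally, a derived value below 1.5 requires a differential below 1.5 × WBC / 100: 0.06% at WBC 4.0 and 0.15% at WBC 10. Virtually every derived count, including a true 0.40, would then default to <1 and normal. The statement that Grade 2 and above are spared holds only after the formula is corrected.

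**Step 4. Where it shows.**
- *Worst post-baseline column of Table 15.3.4.3:* a subject is counted once, at the worst grade. A subject with any other value graded 1 or higher keeps that grade. Only subjects whose worst value is a derived Grade 1 move.
- *Baseline row:* a derived Grade 1 baseline is placed in <1. Such subjects can be enrolled, since Protocol 4.1.1 asks only for a neutrophil count of at least 1.5 ×10⁹/L.
- *Listing 16.2.8.1.1:* each derived Grade 1 visit value carries the wrong grade.
- *Grade 3 or 4 listings:* not affected by the default sentence itself.

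**Step 5. How often.** Not stated. SAP 5.2.2 and Protocol 9.7 list the absolute neutrophil count within the differential, and the protocol needs it for eligibility and for patritumab dosing. Derived neutrophil counts should therefore be uncommon. The documents do not settle whether absolute lymphocyte counts are routinely supplied.

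**The case against.** The best defence is that the rule has a reason. If Grade 1 is bounded by the laboratory's lower limit, and a derived count comes without one, Grade 1 cannot be assigned. That stands as an explanation for not assigning Grade 1. It does not justify calling the value normal; it justifies calling it undetermined. The neighbouring rule for liver tests reported only as below a threshold also defaults to grade <1 and normal, but there a low result raises no concern. Here the default band contains the abnormal values.

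It is also fair to say that the consequence is small. Safety analysis is descriptive, clinically significant laboratory abnormalities are recorded as adverse events in any case, and the listing prints the numeric result beside the grade. All of that stands and is why this is a minor point.

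A reader might infer more than the documents support:
- *That cisplatin dosing is affected.* Protocol Table 5.5 does use the boundary ("Grade 2 or 3: cisplatin treatment delay until < Grade 1"), but that instruction is addressed to investigators at the time of treatment. No SAP tabulation rule feeds back into it.
- *That the shift table would show incomplete recovery as normal.* It shows baseline against worst grade and does not display recovery. Only by-visit output could.
- *That one treatment arm is favoured.* The rule is identical in both arms, and nothing in the plan suggests that derived counts are commoner in one.

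**Conclusion.** The point holds as a defect of a stated rule. For every derived neutrophil or lymphocyte value, Grade 1 is unavailable, and a normal-range statement is made without a range. This contradicts the CTCAE grading both documents promise and the categories of Table 15.3.4.3.

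Per value, the misgrading of derived Grade 1 results is complete. Per subject, it is limited to those whose baseline or worst post-baseline value is a derived Grade 1. No share of records or subjects can be given, because the frequency of derivation is not stated; any percentage would be a guess. The numerical illustrations rest on the assumed neutrophil limits in the working; the conclusion itself does not.

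It would be too strong to read this sentence alone as hiding moderate or severe cytopenia. That would come from the inverted formula, a separate error in the same paragraph. Because the two compound, they should be corrected together.

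**What to change.** In SAP 8.3.2, change the derivation to WBC × differential (%) / 100, and replace the default sentence with:

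> Derived values below Grade 2 will be graded against the reporting laboratory's lower limit for the absolute count where on file; otherwise they will be shown as 'Grade ≤1, limit not available' and will not be flagged as within normal range. For worst-grade selection this category ranks below any value graded 1 or higher and above <1.

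Add the category to Table 15.3.4.3 as both a baseline row and a post-baseline column, and use the same label in Listing 16.2.8.1.1.

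The cost is one formula, one sentence and one extra table category. No endpoint, sample size or clinical rule changes. The downside is a small category that cannot be split into <1 and 1. It may hold most derived values below Grade 2, since a laboratory that reports no absolute count may have no absolute-count limit on file.
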